**3. Abstract:**

Increasing numbers of veterans are experiencing executive dysfunction due to a mild traumatic brain injury (mTBI). Executive dysfunction interferes with participation in home and work activities. Therefore, an effective intervention is needed that will provide significant and long-lasting improvement in the everyday lives of our veterans. Goal Management Training (GMT), an intervention that teaches a five-step strategy to improve planning and organization, has demonstrated promising results (Levine et al., 2000; 2007). However, there are several weaknesses regarding validation of the GMT in individuals with TBI. Therefore, the proposed study is needed to determine the effect of the 10-session GMT on veterans with mTBI. This study will 1) administer the 10-session GMT to individuals that have an objective executive dysfunction; 2) due to mTBI; 3) use probes designed to measure the activities trained in GMT, along with a measure of generalization; and 4) determine the number of subjects needed to demonstrate a treatment effect in a future randomized clinical trial.

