### **Aim 1.**

#### **Aim 1 is to test the benefits of GMT for improving executive function.**

Hypothesis 1a: GMT will significantly improve problem solving ability compared to the control group (primary measure: time to completion on the Tower of London (cTOL). Since PTSD is prevalent and a potentially influencing co-morbidity, we will investigate whether there is a significant interaction between treatment group and PTSD severity.

Secondary measures include number of optimal moves on the TOL; and measures derived from the Stop Signal Task (SST; a measure of inhibition control).

Exploratory Hypothesis 1.a. GMT will significantly improve everyday activities that require executive function skills (primary measure: Behavior Rating Inventory of Executive Function-Adult version, secondary measure: CRIS).

**Analysis Plan for Hypothesis 1. and Hypothesis 1.a.** To test the first specific aim (hypothesis 1), the primary analysis will use two sample t-test to compare group A (intervention) and group B (control) on improvements in time to completion on the TOL. In addition, as an exploratory analysis, we will perform a regression analysis that includes treatment group, PTSD severity and their interaction as independent variables, to adjust for PTSD severity and to investigate whether there is interaction between treatment group and PTSD severity. Similar analyses will be performed for hypothesis 1 for secondary outcome variables of change in index of optimal moves on the TOL and reaction time (RT) and accuracy on SST. To test hypothesis 1a, exploratory *tertiary analysis* using paired t-tests will determine whether treatment effect generalizes to executive function performance in everyday activities (BRIEF-A) or engagement in community participation (CRIS).

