## **6. Research Plan:**

To determine the effect of GMT on veterans with mTBI the following research will be conducted. Clinical staff from the NF/SG VHS will hand out recruitment flyers or refer OEF/OIF/ONF veterans diagnosed with mTBI to the Principal Investigator. Referred Veterans will be contacted by the PI or interested Veterans will contact the PI. Veterans that meet the inclusion/exclusion criteria will be scheduled to obtain consent. Once

consent has been obtained the veteran will be scheduled for the first screening visit. Veterans that meet inclusion criteria will be randomly assigned to either treatment or control groups, in a ratio of 38:16. In addition, the Pocock-Simon covariate adaptive randomization procedure will be used so that, for each PTSD severity category within each of the two sites, approximately 70% (38/54) of subjects are assigned to treatment group; consequently, there will be approximately equal proportion of PTSD subjects assigned to the treatment and control groups within each of the two study sites. Each veteran will complete testing prior to a 10-week intervention or control period; after intervention or control period; and at a one-month follow-up. Intervention will be offered to participants in the control group once testing is complete.

Participants will also be recruited and run in a parallel study in Durham under a Durham VA IRB approval. A total of 168 participants are anticipated to be enrolled in both Gainesville and Durham. Data from Durham will be entered in a VA share drive that both Gainesville and Durham staff can access. Data will not be transferred.

Table # 2 Study Design

	1 st Measure	GMT/Wait	2 nd Measure	3 rd Measure
Group A (n=38)	Pre-treatment testing	GMT/FP 10 wks	Post-treatment testing	Follow-up testing
Group B (n=16)	Pre-Control testing	Control (Brain Health Workshop) 10 wks	Post-control testing	Follow-up Control testing

Methods

Subjects

*Proxy/Informant: patient will select a person to answer a questionnaire on their executive function that observes the patient at least 2-3 times a week and is at least 18 years of age.*

Patient Inclusion Criteria:

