Primary Outcome Measure: Tower of London (TOL): is a computerized program in which patients are shown two pictures simultaneously of a goal board and a test board (Unterrainer et al, 2006). Each picture shows three balls of different colors arranged on three pegs, with the balls in a unique arrangement in each picture. Patients are instructed to determine the fewest possible moves of the balls in the test picture to make the

arrangement of balls identical to that of the goal picture within 60 seconds. The screen reports whether the response is correct or incorrect. Test administration is less than 45 minutes for each session (pre/post/follow-up). Each set consists of 70 problems of variable difficulty, determined by variables, such as, the number of moves needed to solve the problem (Berg and Byrd, 2002). In turn, each set consists of the same number of 4, 5, 6 or 7 move problems and has the same average difficulty level. Difficulty rating is based on global and specific problem parameters shown to affect the planning process (Kaller, 2007, 2008, 2009; Berg, Byrd, McNamara, & Case, 2010; Kaller, Unterrainer, Rahm, & Halsband, 2004). The dependent variables are the total time spent solving the problem and the optimal moves made toward the goal display.

Based on our previous studies, executive function represents three factors (behavior regulation, emotional regulation and metacognition) (Waid, Wen, Heaton, andVELOZO, submitted to Neuropsychology). GMT is a metacognitive training with emphasis on planning prior to engaging in a complex task. Therefore, a primary measure that captures the planning and problem solving of a multi-step task, called the Tower of London (TOL), was selected. Based on results from our preliminary study, the dependent variables of total time and optimal moves will be used to determine treatment effect. While, not all of the participants in our previous work demonstrated significant improvement on these variables, group differences based on paired T-tests were significant in Total Time ( $p=0.026$ ) and Optimal Moves ( $p=0.022$ ) from baseline to treatment. In addition to our findings, Levine (2011) demonstrated a significant change in the TOL following GMT for a mixed neurological sample compared to a control group. Thus, the TOL appears to be sensitive to the effects of GMT.

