### **Aim 1.**

**Aim 1 is to test the benefits of GMT for improving executive function.**

Hypothesis 1a: GMT and home practice device will significantly improve problem solving ability compared to the control group (primary measure: time to completion on the Tower of London (cTOL). Since PTSD is prevalent and a potentially influencing co-morbidity, we will investigate whether there is a significant interaction between treatment group and PTSD severity. Secondary measures include number of optimal moves on the TOL; and measures derived from the Stop Signal Task (SST; a measure of inhibition control).

Exploratory Hypothesis 1.b. GMT and functional practice will significantly improve everyday activities that require executive function skills (primary measure: Behavior Rating Inventory of Executive Function-Adult version, secondary measure: CRIS).

**Analysis Plan for Hypothesis 1.a. and Hypothesis 1.b.** To test the first specific aim (hypothesis 1a), the primary analysis will use two sample t-test to compare group A (intervention) and group B (control) on improvements in time to completion on the TOL. In addition, as an exploratory analysis, we will perform a regression analysis that includes treatment group, PTSD severity and their interaction as independent variables, to adjust for PTSD severity and to investigate whether there is interaction between treatment group and PTSD severity. Similar analyses will be performed for hypothesis 1 for secondary outcome variables of changes in index of optimal moves on the TOL and reaction time (RT) and accuracy on SST. To test hypothesis 1b, exploratory *tertiary analysis* using paired t-tests will determine whether treatment effect generalizes to executive function performance in everyday activities (BRIEF-A) or engagement in community participation (CRIS).

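### The primary comparison of TOL improvement names no visit, and no planned analysis uses the randomised one-month data

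*Combined protocol and SAP*

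**What the plan says.** Section 6 (Research Plan) schedules testing before the 10-week period, then "after intervention or control period; and at a one-month follow-up". Table 1 repeats the TOL, Stop-Signal Task, BRIEF-A, CRIS and other measures at the post-treatment and one-month visits. The same section says: "Intervention will be offered to participants in the control group once testing is complete".

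The primary analysis, in near-identical words in Section 5 (Aim 1) and Section 7 (Aim 1), is a two-sample t-test between the intervention and control arms "on improvements in time to completion on the TOL". No visit is attached to it. None is attached to the secondary analyses (optimal moves, Stop-Signal Task) or to the paired t-tests on BRIEF-A and CRIS. The Aim 2 regression takes TOL time as its dependent variable without naming a visit or saying that it is a change. Neither Section 5 nor Section 7 mentions the one-month visit in any hypothesis or analysis.

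The abstract describes the need as an intervention giving "significant and long-lasting improvement in the everyday lives of our veterans".

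**The concern.** A primary endpoint needs a measure, a time point and a direction. Here only the measure is fixed.

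- **Visit.** With two post-baseline scores, at least two primary results fit the wording: change to post-treatment and change to one month. The mean of the two would fit as well. If the choice is not settled before the data are seen, the nominal error rate is not guaranteed.
- **Direction.** The plan does not say whether a shorter or a longer TOL time is improvement. This is not idle: Section 4 (Background) reports that in the earlier randomised test of the one-hour GMT, improvement on paper-and-pencil tasks meant taking longer, read as greater care.
- **Follow-up.** The design protects a randomised comparison at one month by holding the offer of GMT to controls until testing ends. The analysis plan gives those data no role, so it pre-specifies no between-arm estimate of whether the effect persists.

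The abstract also says the study is to inform the size of a future trial. An effect size for that purpose has to belong to a stated visit.

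**Working it through.** **Plan's own figures.** The documents give no alpha, sidedness, power, effect size or between-visit correlation, so there is no stated figure to reproduce. The allocation check is 38/54 = 70.4%, which agrees with the approximately 70% in Section 6.

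**Inputs.** From Section 6: 38 GMT and 16 control participants, and two post-baseline visits. Assumed: two-sided 5% test, normal change scores, and correlation ρ between change at post-treatment and change at one month, from 0 to 0.9.

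**Step 1: worst-case error if either visit may serve.** Let Z1 and Z2 be the test statistics at the two visits, standard normal under the null with correlation ρ. The chance of at least one significant result is 1 − P(|Z1| < 1.96 and |Z2| < 1.96). At ρ = 0 this is 1 − 0.95² = 9.75%. For other values the bivariate normal distribution gives:

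| ρ | Either visit significant | Of which at least one favours GMT |
|---|---|---|
| 0 | 9.75% | 4.9% |
| 0.5 | 9.1% | 4.5% |
| 0.7 | 8.3% | 4.2% |
| 0.8 | 7.8% | 3.9% |
| 0.9 | 7.0% | 3.5% |

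The last column is 1 − P(Z1 < 1.96 and Z2 < 1.96), against 2.5% for one fixed visit. Simulating the pooled t-test at 38:16 (52 degrees of freedom, 200,000 trials) gives 9.8%, 9.1%, 8.5%, 7.8% and 7.1% for the middle column. If the mean of the two visits is also allowed, the figures are 11.6% at ρ = 0, 8.7% at 0.7 and 7.2% at 0.9.

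**Step 2: how often the two visits would disagree.** At 38:16, a standardised difference of 0.85 gives 80% power (noncentrality 0.85 × √(38 × 16/54) = 0.85 × 3.355 = 2.85). Take that as the true effect at post-treatment, with ρ = 0.7:

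| Effect retained at one month | Power at one month | Visits disagree on significance |
|---|---|---|
| 100% | 80% | 18% |
| 75% | 56% | 30% |
| 50% | 29% | 52% |

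So which visit is meant can change the conclusion even when GMT works.

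**Step 3: what baseline adjustment offers.** Let r be the correlation between pre and post TOL time, with equal variance σ² at both visits (assumed). A change score has variance 2σ²(1 − r). The baseline-adjusted residual has variance σ²(1 − r²). The ratio of adjusted to change-score variance is (1 + r)/2, which is 0.75 at r = 0.5, 0.85 at r = 0.7 and 0.95 at r = 0.9. Adjustment is therefore at least as precise as the change-score t-test, apart from one degree of freedom.

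**Step 4: cost of the alternative.** Making the visits co-equal with Bonferroni (2.5% each) would raise the difference detectable with 80% power from 0.85 to 0.94. Testing them in a fixed order avoids that cost for the primary contrast.

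**The case against.** The strongest reply is that post-treatment is plainly meant. Table 2 labels the second measure as post-treatment testing and the third as follow-up. The TOL description in Section 6 justifies the outcome by a preliminary study whose contrast ran from baseline to treatment. This stands as evidence of intent, but the preliminary study is not this trial's plan, and neither analysis section states the visit.

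Three stronger readings are tempting, and the documents do not support them.

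- **That the plan runs at 8% or 9% error.** Those rates need an analyst to test both visits and report whichever is significant, and nothing in the documents suggests this. Nor can that harm occur together with unused follow-up: if the one-month data are never tested, there is one contrast and no inflation.
- **That the trial fails a durability objective.** The long-lasting wording describes what veterans need. Neither aim contains a maintenance hypothesis, and one month would be limited evidence of lasting benefit.
- **That participants who miss the post-treatment visit but attend at one month are a material loss.** The documents give no dropout figure, so the size cannot be judged.

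It is also fair to say that this is a self-described Phase I study with 16 controls, and that naming the visit alone, with the t-test kept, would close the main gap.

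**Conclusion.** The point holds as an under-specified primary contrast and a randomised follow-up comparison with no planned use. Post-treatment is the likely intended visit, so the practical ambiguity is smaller than two equal candidates would imply. The exposure is a worst case of about 7% to 10% two-sided false positives, with about half of the errors favouring GMT. It rests on an assumed two-sided 5% test, normal scores, a between-visit correlation from 0 to 0.9, and a choice of visit made after seeing the data. The disagreement rates of 18% to 52% further assume a true post-treatment effect of 0.85 SD and a correlation of 0.7.

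This should be corrected before analysis. It does not invalidate the design: the data needed are already being collected, and the remedy improves precision as well as clarity.

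**What to change.** In Section 7, and in the matching text of Section 5:

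1. Name the change from pre- to post-treatment in TOL time as the primary contrast, and state whether a shorter or a longer time counts as improvement.
2. Replace the unadjusted change-score t-test with a baseline-adjusted arm comparison. Either use ANCOVA at post-treatment, or fit one mixed model with post-treatment and one-month scores as responses, the pre score as covariate only (not also as a response), arm-by-visit terms, and a small-sample degrees-of-freedom correction.
3. Report the arm difference at one month as a named secondary contrast, tested only if the primary is significant.
4. Do the same for the secondary outcomes.

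The cost is SAP wording and slightly more modelling than a t-test. No new visits or data are needed.

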### *Procedures*

Intervention: The GMT is a 7-session intervention has been modified to a 10-session (2 hours/ session) interactive Power Point module that is presented in an individual or group format. Sessions 5, 6 and 7 have been split into two sessions each with time added to set-up and review functional practice. If a group format, the subject will be incorporated into a therapy session with 3-5 other participants (either other clinical patients or research participants diagnosed with TBI). During each session, a 5-stage strategy is taught to the participants. The 5-stage process consists of “stop-what am I doing?”, “define the goal”, “list the steps”, “learn the steps” then “check-am I doing what I planned”. The strategy is then incorporated into tasks practiced in the group session as well as in tasks each participant is to practice at home. The participants discuss utilization of the strategies and support the other members in the group. Friends or family members will participate in a training session prior to beginning GMT with the subject. The family member will be called each week during the GMT and asked to report whether the subject had an easy or difficulty time completing the homework assignments each week.

*Simulated Practice In The Laboratory:* Tasks during GMT training include exercises such as: 1) clapping to words while inhibiting clapping to a targeted word; 2) card sorting; 3) decision making and planning in order to complete five activities within a four minute time span; 4) Catalog Task; and 5) Book keeping task. The exercises start with relatively easy tasks and progress to more complex tasks. Participant’s strengths and weaknesses are discussed. Improvements are identified and reinforced as they learn more efficient planning and problem solving. The following steps are taught during simulated tasks: 1) Identify Main Goal; 2) Break down task into sub-goals and steps for each goal; 3) List supplies needed; 4) Recognize potential barriers to completing goal; 5) Determine strategy to accomplish task; 6) Prepare to begin task with “presence of mindedness” exercise; 7) State goal out loud; 8) Begin task and stop self frequently to state main goal out loud and check to be sure one is working toward the goal (on target).

*Functional Practice with Smartphone Technology:* In addition to GMT in the lab, three tasks will be first practice in the lab, than practiced at home. Participants will

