select from the following: meal planning and shopping; planning a party; building a birdhouse; or paying monthly bills. A Smartphone application (AP) specifically developed to utilize the strategies taught in GMT will be loaded onto the participant's Smartphone (iPhone, iTouch, or Droid). Veterans that do not already possess one of the devices will receive one as part of their clinical service through prosthetics. Training will begin during the first session to learn the features of the technology they will need (calendar, list, alarms) using Michelle Wild's standardized learning procedure outlined in her guide books (<http://pda4memory.com>) that have been designed to train individuals with TBI how to use Smartphones. Participants will use the application features to break down tasks, estimate time to complete, check off each step as completed, respond to visual/vibrating alert of "Goal" and respond to alert if "On Target". Information, such as accuracy of planned steps, time to complete task, and number of distractions from goal will be collected by the AP. Data will not be electronically transferred; the participant's performance in functional practice at home will be reviewed and documented at the next lab session.

*Control Group Intervention.* The Brain Health Workshop (BHW; Levine 2011) was developed specifically for consistency with GMT session length and contact with the facilitator (Levine, 2011). BHW is an education presentation on brain function and cognitive principles of learning. Information about stress reduction, sleep hygiene, energy management, exercise and communication are covered, with homework and quizzes on information covered.

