#### Exploratory Generalization Measure

Generalization measures will be examined in a tertiary analysis to explore whether treatment effects generalize to everyday activities or participation in the community. Based on our previous study, treatment effect did not generalize to everyday activities as measured by the BRIEF-A. However, with the proposed methodological changes and the addition of functional practice with a Smartphone application, generalization to activities and community participation is anticipated to improve. The Metacognitive Index of the BRIEF-A was confirmed as a factor in our previous factor analysis and represents the executive function components targeted by GMT. The BRIEF-A was selected over the recommended common data element measure, the Frontal Systems Behavior Scale (FrSBe); since the FrSBe has not been tested in a homogenous TBI sample. While, our previous study did not reflect a significant improvement at the activity level, we will conduct a tertiary analysis to detect generalization using the BRIEF-A. In addition to the activity level of executive function, we would like to determine the effect of treatment at the community participation level. The TBI Outcomes Workgroup on common data elements (Wilde, 2010) has recommended the PART-O to measure participation in the community.

Behavior Rating Inventory of Executive Functions–Adult (BRIEF-A) is a self and informant report questionnaire consisting of 75 statements about executive behaviors. There are three possible responses to items: often, sometimes, never. There are nine subscales: inhibit, self-monitor, plan/organize, shift initiation, task monitor, emotional control, working memory, and organization of materials. Normative self-report (n=1,050) reliability ranges from .73 to .90 for the scales and .93 to .96 for Index and Global Executive Composite scores. While the reliability in a mixed clinical sample (n=233) ranged from .80 to .94 for scales and .96 to .98 for Index and Global Executive Composite scores. Test-retest reliability over 4 weeks averaged .82 to .93 on the scales and .94 for Index and Global Executive Composite

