scores. The total BRIEF-A score correlates at .84 with the Dysexecutive Questionnaire (Roth, 2005). In a sample of patients diagnosed with TBI, the MI reported a Cronbach alpha of 0.96 (Waid-Ebbs et al., 2012). The Metacognitive Index of the score of the BRIEF-A will be used to detect a change of executive functioning in the subject's home environment.

Community Reintegration of Service Members (CRIS): will be used to measure participation. The CRIS was developed specifically for soldiers with disabilities (Resnik et al., 2009, 2011) and is available in two formats, a paper and pencil version with 128 items and a computer adapted version that takes no more than 10 minutes to complete. Three scales are found in the CRIS and have good internal reliability: Extent of Participation = 0.91, Perceived Limitations = 0.93, and Satisfaction with Participation = 0.97 (Resnik et al, 2009). Meaningful detectable change indices were 5.9, 6.2, and 3.6, respectively for Extent, Perceived and Satisfaction subscales (Resnik et al, 2012). CRIS-CAT scores were predictive of SF-12 physical and mental health related quality of life scores at the 1-year follow-up (Resnik et al, 2012). Preliminary analysis described reveals good internal reliability and separation into ability levels in a sample of 44 mTBI Veterans. Test Retest reliability is 0.95 for Extent of participation; 0.85 for Perceive limitation; and 0.95 for Satisfaction scales.

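### BRIEF-A and CRIS generalisation is judged by paired t-tests with no between-arm comparison, so a change shared by both arms could be read as a GMT effect

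*Combined protocol and SAP*

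**What the plan says.** The Aim 1 analysis plan appears in section 5 (Specific Aims) and again in section 7 (Statistical Methods), and on this point the two agree. BRIEF-A and CRIS go to an exploratory tertiary analysis "using paired t-tests will determine whether treatment effect generalizes to executive function performance in everyday activities (BRIEF-A") or to community participation on CRIS. Neither section says which participants enter the paired tests or which two visits are paired.

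The same paragraph treats the primary outcome differently: "the primary analysis will use two sample t-test to compare group A (intervention) and group B (control) on improvements in time to completion" on the Tower of London (TOL). That matches Hypothesis 1a, which states that GMT "will significantly improve problem solving ability compared to the control group". The sentence extending similar analyses to other outcomes covers only TOL optimal moves and the Stop Signal Task. The hypothesis on everyday activities names no comparator.

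Other relevant text:
- Section 6, Research Plan: "Each veteran will complete testing prior to a 10-week intervention or control period; after intervention or control period; and at a one-month follow-up". Table 1 lists BRIEF-A and CRIS before treatment, after treatment and at one month.
- Section 6, Control Group Intervention: the Brain Health Workshop "was developed specifically for consistency with GMT session length and contact with the facilitator".
- Section 6, Exploratory Generalization Measure: "Based on our previous study, treatment effect did not generalize to everyday activities as measured by the BRIEF-A". Improvement is now anticipated because of methodological changes and the added functional practice. For the score, "The Metacognitive Index of the score of the BRIEF-A will be used to detect a change of executive functioning".

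**The concern.** Within-person change is not a treatment effect. It contains whatever GMT does, plus anything that moves scores in both arms: time, retesting, expectation, facilitator contact, regression to the mean. A randomised control arm exists to remove that shared part, and this one was built to match session length and contact. For everyday function the plan collects the control data and names no test that uses them.

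If both arms improve equally, following the plan as written could still lead to the conclusion that the GMT effect generalises. That conclusion would matter. The previous study found no generalisation on BRIEF-A, so a positive result here would naturally be credited to the changes made since then and carried into the later randomised trial that this study is meant to inform.

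**Working it through.** **Which test is meant.** Paired cannot be read as group A versus group B. The arms are unequal (38 and 16), no matching of individuals is described, and the same paragraph says two-sample when it means A versus B. Aim 2 does state its analysis set (intervention participants only); the BRIEF-A and CRIS analysis states none. Three readings are therefore open: group A alone, each arm separately, or both pooled.

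**Inputs from the documents.** Table 2 gives 38 and 16, total 54; 38/54 = 70.4%, which agrees with the stated allocation of about 70%. The documents give no alpha, SD, effect size or power for BRIEF-A or CRIS, so there is no planned figure to reproduce.

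**Assumptions, not in the documents.** Two-sided 5%; normal change scores with equal SD in both arms; no exclusions; zero GMT effect; the same shift d (in SDs of the change score) in both arms.

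**Paired test.** It rejects when |t| exceeds t(0.975, n−1), where t is noncentral with parameter d√n. For group A at d = 0.3: 0.3 × √38 = 1.849, critical value 2.026, rejection probability 0.437.

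| Shared shift d | Group A, n=38 | Group B, n=16 | Pooled, n=54 | A significant, B not | Two-sample, 38 vs 16 |
|---|---|---|---|---|---|
| 0 | 5% | 5% | 5% | – | 5% |
| 0.1 | 9% | 7% | 11% | 8% | 5% |
| 0.2 | 22% | 12% | 30% | 20% | 5% |
| 0.3 | 44% | 20% | 58% | 35% | 5% |
| 0.5 | 85% | 46% | 95% | 46% | 5% |

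The fifth column is P(A significant for improvement) × P(B not significant), since the arms are independent. Separate tests in each arm therefore do not solve the problem: with the same change in both, the larger arm often reaches significance when the smaller does not.

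In the two-sample test the shared shift cancels, so its rejection rate is 5% for any d. Simulation of 40,000 trials per shift agrees: 22.7%, 43.4% and 85.1% for the paired test in group A at d = 0.2, 0.3 and 0.5, against 5.1% each time for the two-sample test.

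If the section 7 exclusions left 34 of the 38 (assumed), the group A rates would be 21%, 40% and 81%.

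**Precision of the between-arm test.** Standard error of the difference = √(1/38 + 1/16) = 0.298 SD. The 95% CI half-width is 2.007 × 0.298 = 0.60 SD. Power is 17%, 38% and 75% at true differences of 0.3, 0.5 and 0.8 SD; 80% power needs about 0.85 SD.

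**The case against.** The strongest reply is that this analysis is labelled exploratory and tertiary in a study described as Phase I, with no alpha or success criterion attached to it. That stands as a limit on severity: nothing here touches the primary TOL comparison. It does not rescue the method. Exploratory status can excuse low power or the absence of multiplicity control, but the plan says these tests will determine whether the treatment effect generalises, and a within-arm test does not estimate that effect.

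Second, the size depends on an assumed shared shift. That is correct. At 0.05 SD the group A rate is 6% and at 0.1 SD it is 9%. Eligibility is set on Color-Word Interference or the Flanker task, not on BRIEF-A or CRIS, and BRIEF-A index retest reliability is given as .94, so regression to the mean may be weak. Expectation and attention effects remain plausible, and the documents do not bound them.

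Third, comparing A with B would not isolate functional practice, which is delivered only with GMT. This also stands: the comparison tests the package. Finally, the arm sizes rest on Table 2, while the Background section gives 40 veterans and the Research Plan anticipates 168 enrolled across sites; the precision figures would move with the analysed numbers.

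**Conclusion.** The concern holds. For BRIEF-A and CRIS the plan specifies within-person tests only, leaves the analysed group unstated, and would let a change common to both arms count as generalisation of GMT. Under the assumptions above, the false-positive rate in group A is 22% to 85% for shared shifts of 0.2 to 0.5 SD, close to 5% if the shift is negligible, and higher if the arms are pooled. A two-sample comparison holds 5% throughout, provided exclusions do not differ by arm in a way related to outcome. This should be fixed, but it is confined to the exploratory outcomes.

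**What to change.** In the Aim 1 analysis plan in both section 5 and section 7, replace the paired t-tests by the group A versus group B two-sample t-test of change already specified for TOL time. Apply it to the BRIEF-A Metacognitive Index and to each of the three CRIS scales. A baseline-adjusted comparison of post scores is an acceptable alternative if one method is named in advance. Report the arm difference with a 95% CI, label it exploratory, and show within-arm change as description only. In the same edit, state the time points compared, whether the patient or informant BRIEF-A is used, and whether the section 7 exclusions apply.

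The cost is wording only, because the data are already scheduled in both arms. The price is precision: with a half-width of about 0.60 SD and 38% power at 0.5 SD, a non-significant result must not be reported as no generalisation.

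One limitation should be stated. Under Procedures, friends or family are trained before GMT, and "The family member will be called each week during the GMT"; no such contact is described for the control arm. The two-sample test would not remove a resulting bias in informant-rated BRIEF-A: an assumed GMT-only bias of 0.3 or 0.5 SD would make it significant in 17% or 38% of trials.
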